7.6 Cytokine Release Syndrome (CRS)

Administration of transgenic T cells such as FH-MCVA2TCR may be associated with CRS. CRS may be characterized by high fever, fatigue, nausea, headache, dyspnea, tachycardia, rigors, hypotension, hypoxia, myalgia/arthralgia, anorexia, coagulation abnormalities, organ dysfunction, and neurologic abnormalities.

If a patient becomes febrile or develops symptoms of CRS, cytokine levels, serum ferritin, C-reactive protein (CRP), coagulation studies, and/or markers of tumor lysis syndrome (e.g., chemistry, uric acid, lactate dehydrogenase [LDH]) may be measured, and persistence and/or phenotype of the transgene-expressing cells may be evaluated, as clinically indicated.

Any patient who develops clinical evidence of symptoms related to CRS will have a work-up to exclude infection or other causes, as clinically appropriate. Initial treatment should consist of supportive measures as dictated by the clinical and laboratory findings, and may include fluid replacement, medications to support blood pressure, antipyretics, oxygen supplementation, anti-seizure medications, and broad-spectrum antibiotics if infection cannot be excluded as a potential etiology for the signs and symptoms.

The 2019 Lee et al consensus guidelines for immune effector cell will be utilized to quantify T cell associated CRS,^{79,80} as detailed in **Appendix E**.

General guidelines for management of CRS are provided in **Appendix F** based on our current institution standard practice. Other cytokine-directed therapies may be considered after discussion with the PI and/or immunotherapy attending.

7.7 Neurologic Toxicity

Neurotoxicity, manifested as delirium, seizures, focal neurologic deficits, and/or coma has been reported after CAR T-cell therapy. Although neurotoxicity has not been reported after transgenic TCR therapy, if neurotoxicity develops management will be given analogous to CAR therapy. Neurotoxicity to CAR-T is usually reversible but can be irreversible or fatal. Neurotoxicity/ICANS will be graded according to 2019 Lee et al consensus guidelines,⁷⁹ as detailed in **Appendix E**.

For patients who develop mild neurologic manifestations (Grade 1), symptomatic care and levetiracetam are recommended. Discussion with the PI or designee is recommended. For patients with worsening neurologic changes, the addition of corticosteroids should be considered (e.g., dexamethasone 10 mg IV every 6 to 24 hours). Tocilizumab (4-8 mg/kg IV) or other cytokine-directed therapies may be used based on clinical judgment; at this time, it is unclear if these approaches are of benefit to patients with neurotoxicity. Cerebrospinal fluid (CSF) assessments and CNS imaging should be considered if clinically indicated.

7.8 Tumor Lysis Syndrome

Although rarely reported for MCC, FH-MCVA2TCR may cause tumor lysis syndrome (TLS) in patients with high disease burden. Patients with large bulky tumors will be considered for allopurinol prophylaxis to start prior to interferon gamma and continued for as long as the medical team determines appropriate after the infusion, unless there are contraindications. Patients may receive additional hydration for the first 2 weeks after infusion. If TLS develops, as defined by the Cairo Bishop criteria,⁸¹ the Attending Physician will direct patient management with guidance from the study staff.⁸² Conservative therapy, including allopurinol and IV fluid hydration may be instituted immediately for suspected TLS. Hyperkalemia may be treated with potassium-binding resins, diuresis, or insulin/dextrose therapy. Hyperphosphatemia may be treated with phosphate-binding resins. In severe cases, rasburicase (in non-G6PD-deficient individuals) or renal dialysis may be necessary.

7.9 Macrophage Activation Syndrome

Macrophage activation syndrome (MAS) is a serious disorder potentially associated with uncontrolled activation and proliferation of T cells and subsequent activation of macrophages. MAS is typically characterized by high-grade, non-remitting fever, cytopenias, and hepatosplenomegaly, and may be difficult to distinguish from CRS. Laboratory abnormalities found in MAS include elevated inflammatory cytokine levels, serum ferritin, soluble IL-2 receptor (sCD25), triglycerides, and decreased circulating NK cells. Other findings include variable levels of transaminases, signs of acute liver failure, coagulopathy, and disseminated intravascular coagulopathy. While there are no definitive diagnostic criteria for MAS, it is typically diagnosed using published criteria for hemophagocytic lymphohistiocytosis.⁸³

Patients treated with FH-MCVA2TCR should be monitored for MAS, and cytokine-directed therapy or corticosteroids should be considered as clinically indicated.

7.10 Adrenal Toxicity

Immune-mediated damage to the adrenal gland is a potential toxicity and could be manifested as primary mineralocorticoid or glucocorticoid deficiency.

If mineralocorticoid and/or glucocorticoid insufficiency should occur, diagnosis may be difficult in the acute setting of CRS, and attention should be given to ensuring there is sufficient replacement therapy.

For patients with hypotension in the absence of fever that is unresponsive to fluid boluses, fludrocortisone or other mineralocorticoid administration should be considered. If CRS requiring intervention with tocilizumab and dexamethasone should occur, the activity of dexamethasone 10 mg/bid will likely be sufficient; however, if hypotension recurs following cessation of dexamethasone or persists despite dexamethasone, stress-dose hydrocortisone is recommended. Samples will be assayed for renin, aldosterone and cortisol levels. To detect subclinical hypoadrenalism, an adrenocorticotrophic hormone (ACTH) stimulation test will be performed at baseline and approximately 4 weeks after infusion.

7.11 Immune mediated adverse events

Avelumab and pembrolizumab are associated with a known risk of irAEs. Patients will be closely monitored for potential irAEs,^{84,85} which may manifest earliest after weeks of treatment. Such events may consist of persistent rash, diarrhea and colitis, autoimmune hepatitis, arthritis, glomerulonephritis, cardiomyopathy, or uveitis and other inflammatory eye conditions. The spectrum of hypothetical irAEs also includes formation of auto-antibodies like anti-nuclear antibodies (ANAs) or antineutrophil cytoplasmic antibodies (ANCA). Severe irAEs will be managed with steroids. Where possible, irAEs definitely, probably, or possibly secondary to avelumab or pembrolizumab will be managed by the Attending Physician in consultation with the study team in accordance with ASCO society guidelines.⁸⁶ Both interferon gamma and avelumab/pembrolizumab can cause GI toxicity. More commonly GI toxicity due to pembrolizumab/avelumab will manifest as diarrhea that is persistent. Persistent diarrhea will be attributed to pembrolizumab/avelumab and managed by the attending physician in consultation with the study team in accordance with ASCO society guidelines. Episodic diarrhea or vomiting associated temporally with interferon gamma administration will be attributed to interferon gamma and managed with dose interruption or cessation in cases of grade 3 or higher toxicity.

7.12 Persistent Uncontrolled T-cell Proliferation

Uncontrolled proliferation of TCR modified T cells has not been observed in clinical trials to date.²⁹ However, in the unlikely event that clinically significant uncontrolled and persistent proliferation of T cells occurs in a study patient, initial therapy may involve treatment with corticosteroids (e.g., methylprednisolone 1 g IV). If there is a progressive increase in TCR T cells to greater than 30% of T cells at more than 3 months after the last infusion is observed, an analysis for clonal expansion by deep sequencing of the T-cell receptor (TCR) beta gene (Adaptive Biotechnology) may be conducted.

7.13 Replication-Competent Lentivirus

All patients will be followed in this study for presence of replication-competent lentivirus (RCL) for up to 15 years following the last dose of FH-MCVA2TCR. Research studies to detect presence and phenotype T cells may be conducted on samples of tissue biopsies or blood performed for clinical conditions occurring during follow-up considered possibly related to FH-MCVA2TCR.

7.14 Management of Other Toxicities

If a new onset CTCAE v5 Grade ≥ 3 toxicity is observed following infusion, the patient will receive investigation and medical treatment appropriate for the physiological abnormalities. Grade ≥ 3 toxicity that is attributed to the infusion may be treated with corticosteroids (e.g., dexamethasone 10 mg IV every 4 to 12 hours), tocilizumab, or other cytokine-directed therapy after discussion with the PI or designee.

8. INFORMED CONSENT OF PATIENT

8.1 Patient screening

An evaluation consent, separate from the treatment consent, will be used for the patient to provide consent for records review, pathology review, MCPyV tumor testing (if previously unknown), and HLA typing. Where possible, consent for evaluation will be performed in person. However, for many patients this will not be possible for travel/logistical reasons. In this case, evaluation consent discussion may be performed by telephone by trained study personnel, and consent documents exchanged by email, mail or fax.

8.2 Treatment

Patients will be seen at Fred Hutch/UWMC for consideration of treatment options for their disease. The protocol will be discussed thoroughly with the patient and other family members if appropriate and all known and potential risks to the patient will be described. The procedure and alternative forms of therapy will be presented as objectively as possible and the risks and hazards of the procedure will be explained to the patient. Consent from the patient will be obtained using forms approved by the Fred Hutch IRB. A summary of the clinic visits detailing what was covered will be dictated for the medical record.

9. PATIENT REGISTRATION

Eligible patients will be identified and registered into the system by the Clinical Coordinator's Office (CCO; Intake Office) and assigned a Unique Patient Number (UPN). The CCO will register the patient for the protocol through the Data Management Office.

Patients will initially be screened. Enrollment to the therapy portion of the study will occur at the conclusion of the pre-T-cell work-up when data are reviewed for all inclusion and exclusion criteria for therapy by the Immunotherapy attending physician and the patient signs consent for therapy.

A study number will be allocated to each patient and a log of enrolled patients will be maintained.

10. TRAVEL REIMBURSEMENT

Patients who consent to the treatment arm of the study will be eligible for limited travel reimbursement of actual expenses incurred, up to \$3,500. Please see consent form for additional details.

11. CLINICAL AND LABORATORY EVALUATIONS

A tabular schedule of events is provided in **Appendix A**. The proposed days of all treatments and assessments are approximate and may vary due to scheduling, clinical or other factors.

11.1 Visits required to be at Fred Hutch/UWMC

Many of the patients with MCC travel >500 miles to receive care at Fred Hutch/UWMC. Although up to two T cell infusions are given, the avelumab is given every 2 weeks for a year (or pembrolizumab every 3 weeks for a year), as a standard of care treatment, using standard of care FDA approved dosing and frequency. Therefore, for interventions surrounding T cell infusions and the first avelumab or pembrolizumab infusion after each T cell infusion, we request care to be at Fred Hutch/UWMC, in order to ensure safety. However, for "maintenance" avelumab or pembrolizumab visits, we will allow patients to receive these infusions with their local/primary oncologist if that is patient preference, except as detailed below.

Leukapheresis, pre-treatment biopsy, and pre-treatment physical exam, and treatment consenting need be performed through Fred Hutch/UWMC.

For cycle 1 of T cell therapy, the patient is required to receive care at Fred Hutch/UWMC and stay within 30 minutes of Fred Hutch/UWMC from the first dose of interferon gamma (day -5) through T cell infusion and the 28-day dose-limiting toxicity (DLT) period thereafter. This period includes the first (d+14) avelumab or pembrolizumab infusion, if eligible/stable. If the patient shows no signs of T cell mediated toxicity within 17 days of T cell infusion (and 3 days for PD-1/PD-L1 inhibitor infusion), they may return to the care of their treating oncologist with permission of the PI.

Day 28, 42, 56, 70, and 84 avelumab (or day 35, 56 and 77 pembrolizumab) may be given locally or at Fred Hutch and research blood may be shipped/mailed. Day +84/cycle 1 evaluations including research and clinical blood work, exams, imaging, and biopsy should be performed if possible at Fred Hutch or UWMC. Patient must remain within 30 minutes of Fred Hutch/UWMC for second T cell infusion and at least 28 days thereafter, during which avelumab or pembrolizumab is likely to be administered.

Subsequent avelumab or pembrolizumab may be given locally. If the patient shows no signs of T cell mediated toxicity within 17 days of T cell infusion (and 3 days for PD-1/PD-L1 inhibitor infusion), they may return to the care of their treating oncologist with permission of the PI.

6 month, 9 month and 12 month imaging and laboratory evaluations are requested to be performed at Fred Hutch; however, they may be performed locally if circumstances preclude travel to Fred Hutch.

11.2 Screening Evaluations

1. Determination of viral status if not previously determined (MCPyV AMERK serology assay and/or testing of archival tumor tissue).
2. HLA Typing (HLA typing will be organized by and billed to study)

11.3 Pre-Treatment Evaluations

Results of tests and procedures conducted as per standard of care purposes prior to screening may be used for research purposes if conducted within the protocol-defined window.

The screening consent and HIPAA authorization must be signed before any non-standard of care evaluations are performed.

Baseline evaluations include:

1. Medical history and physical examination including prior therapies and response to therapy if known, and Karnofsky performance status.
2. Laboratory tests, including:
 - a. CBC, differential, platelet count
 - b. Comprehensive metabolic panel
 - c. LDH
 - d. Fred Hutch (PSBC) Donor Battery Panel (should be performed within 30 days of leukapheresis)
 - e. Serum ferritin
 - f. Serum CRP
 - g. Uric acid

- h. Serum IL-6
- i. Prothrombin time (PT), partial thromboplastin time (PTT) (should be performed within 30 days of leukapheresis)
- j. Serum pregnancy test for females of childbearing potential within 14 days of planned leukapheresis.
3. Confirmation of diagnosis by internal pathology review of initial or subsequent biopsy or other pathologic material at Fred Hutch.
4. Baseline pulse oximetry and documentation of O₂ saturation on room air
5. Baseline 12-lead EKG
6. Patients age 60 years or older: Echocardiogram or MUGA scan
7. Baseline imaging (generally CT chest/abdomen/pelvis (and if present affected extremity), MRI brain if history of brain metastasis or neurologic symptoms, CT neck if prior cervical adenopathy, MRI or PET may be substituted as clinical judgement dictates). Imaging must be obtained within 45 days of prior to start of first planned FH-MCVA2TCR infusion
8. For skin/cutaneous tumors, representative/target tumors should be photographed pre treatment for baseline measurements (optional).
9. Clinical documentation of relapsed disease (imaging and/or biopsy).

Research samples:

1. PBMC Baseline Samples: A 60 ml blood sample (in EDTA [lavender top] tube) for research should be sent to the Specimen Processing/Research Cell Bank lab at the Fred Hutch for PBMC isolation and cryopreservation. These cells will be used as PBMC baseline samples for comparison to post-treatment samples for all cellular correlative tests, including T cell persistence and immunophenotype by flow cytometry or Q-PCR or TCR-β deep sequencing (Adaptive Biotechnologies) assays, assessment of anti-transgene, and anti-tumor immune responses. These tests are all optional and may be performed depending on tumor response and T cell persistence.
2. Baseline serum: A 20 ml blood sample (serum separator tube) should be sent to the Specimen Processing/Research Cell Bank lab at the Fred Hutch to be used as serum baseline to assess anti-transgene and anti-tumor immune responses. These tests may be performed depending on tumor response and T cell persistence.
3. Other biopsy or sample: If biopsy or sampling of tissues other than bone marrow (i.e., CSF, pleural fluid, etc.) is performed for clinical indications, then additional tissue may be obtained during the same procedure and sent to the Specimen Processing/Research Cell Bank Lab at the Fred Hutch for research studies. Please discuss the planned procedure with the study PI.
4. RCL Testing: A 10 ml (EDTA/lavender top) blood sample should be collected as baseline before both cycles 1 and 2 for RCL testing and sent to the Specimen Processing Lab/ Research Cell Bank Lab at the Fred Hutch.
5. Research RECIST 1.1 read of baseline scans
6. Biopsy samples: If clinical biopsy performed within 42 days of study enrollment documenting persistent/progressive MCC and research samples not collected, a core needle (6 needle passes) or punch biopsy (1 x 6 mm or 2 x 4 mm) or equivalent sample will be collected for research if clinically feasible. Where possible, research samples will be coordinated with clinical biopsies.

11.4 Evaluations prior to T cell Infusion

On the day of scheduled T cell infusion, the patient should undergo a clinical evaluation and a clinical determination for appropriateness to proceed with T cell administration.

1. Interval history and physical exam
2. Research biopsy to evaluate class I MHC upregulation
3. Blood draw for laboratory studies:
 - CBC, differential, and platelet count
 - Comprehensive metabolic panel
 - LDH
 - Uric acid
 - Research Labs: Cytokine levels (research); T cell baseline persistence, function

11.5 Evaluations following T cell infusion

The following evaluations will be performed after the T cell infusion.

1. Record new findings on history and physical exam 1 day after the T cell infusion and at least weekly for 3 weeks.
2. The following laboratory studies at least twice weekly for 2 weeks, then weekly until 4 weeks after the T cell infusion:
 - a. CBC, differential, and platelet count
 - b. Comprehensive metabolic panel
 - c. LDH
 - d. Uric acid
3. If patients become febrile or develop symptoms of cytokine release or tumor lysis between the indicated time points, we may measure serum ferritin, IL-6, CRP, DIC panel, and tumor lysis markers at additional times, as clinically indicated.
4. Tumor biopsy: between approximately 10 to 16 days following the T cell infusion, all patients with pathologic, palpable or radiologically accessible lymphadenopathy will be asked to undergo a punch, excisional or a core biopsy of an accessible tumor. The biopsy at 2-week time point will be for research. The requirement for a biopsy will be waived for patients who do not have tumor amenable to biopsy. Patients will also be asked to undergo a biopsy at time of 12-week re-evaluation and may also be asked to undergo a tumor biopsy at the time of relapse. The goal of the 12 week biopsy will be to confirm that there is progressive/residual tumor if tumors are stable or growing (pseudoprogression has been reported at up to 3 months in the JAVELIN trials of avelumab for MCC), and to confirm that there is residual tumor if tumors are shrinking (would not give second T cell infusion if no residual viable tumor). The purpose of the repeat biopsy at time of late relapse would be to confirm that the relapsed lesion represents MCC. These 12-week and relapse biopsies will thus be clinical with additional portion/core for research.
5. Research labs:
 - a. Leftover materials will be archived for future studies of T cell function. All research assays are optional and may be performed or omitted or replaced with similar studies based on patient's clinical course.
 - b. Serum storage for measurement of serum cytokine levels

- i. Serum cytokine levels. Serum should be collected in serum separator tube at volumes indicated. Samples should be sent to the Specimen Processing/Research Cell Bank Lab at Fred Hutch. Serum cytokine levels will be run at selected time points (optional).
- ii. If patients become febrile, develop signs of CRS, or cytokine assessment is clinically appropriate at times other than those indicated, we may measure cytokine levels at additional times (optional).
- c. Evaluation for persistence and phenotype of **TCR transgenic** T cells
 - i. PBMC for TCR T cell persistence: Blood samples (EDTA [lavender top] tube) should be obtained on approximately days 1, 3, 7, 14, 21, and 28 during the first month after the T cell infusion, and also at 2, 3, 6, 9, and 12 months after the T cell infusion for analysis of the persistence and phenotype of transferred T cells. Samples should be sent to the Specimen Processing/Research Cell Bank Lab at Fred Hutch. Additional samples may be collected at other times than those indicated, including beyond 12 months, if required for evaluation of persistence of TCR T cells. Conversely, persistence monitoring may be discontinued beyond day 28 after each infusion in patients who do not have detectable transgene-expressing T cells on two consecutive occasions. The cells from these blood samples may also be analyzed by multiparameter flow cytometry for the phenotype of persisting TCR T cells (optional).
 - ii. If patients become febrile, develop possible signs of toxicity, or assessment of TCR T cell persistence is clinically appropriate at times other than those indicated, we may measure the persistence of transferred T cells at additional times.
- d. Evaluation of migration of adoptively transferred **TCR** T cells
 - i. Single cell tumor digests will be generated from research biopsy tissue and for selected patients single cell RNA sequencing will be performed (optional).
 - ii. Multiplex immunohistochemistry will be performed on clinical and/or research biopsies to evaluate T cell localization (optional).
- e. Evaluation for development of endogenous anti-tumor immune responses and epitope spreading

We may evaluate whether any cellular or humoral anti-tumor immune responses resulting from activation of endogenous immune cells have occurred. For this purpose, we will collect the following. Additional and/or fewer time points may be performed. Research samples will be collected; however, performance of research studies is optional and assays may be substituted with alternate assays or omitted as clinical course dictates.

 - i. Serum anti-tumor immune responses: Serum for humoral immune responses around day 14, and at approximately 3, 6, and 12 months after T cell infusion to the Specimen Processing/Research Cell Bank lab at Fred Hutch. This is for full serologic panel testing for research purposes and is separate from the clinical AMERK MCPyV serology.
 - ii. PBMC anti-tumor immune responses: (lavender top tubes) for cellular immune responses around day 14, and at approximately 3, 6, and 12 months after T cell infusion to the Specimen Processing/Research Cell Bank lab at Fred Hutch
 - iii. T-cell repertoire by deep sequencing: Blood (10 ml EDTA [lavender top] tubes) around day 14, and at approximately 3 and 6 months after the T cell infusion to the Specimen Processing/Research Cell Bank lab at Fred Hutch to evaluate the T-cell repertoire by deep sequencing of TCR- β sequence

Whole exome sequencing and RNA Seq: For patients in whom endogenous immune responses are detected, more detailed evaluation may be performed to characterize T cell

responses by predicting which tumor mutations are likely to be immunogenic and then evaluating peripheral blood T cells for reactivity to these epitopes. To identify mutations and determine the patient's HLA alleles, whole exome sequencing and RNA Seq of baseline tumor as well as whole exome sequencing of normal tissue may be performed (optional).

f. RCL testing

Blood samples should be collected at approximately 3, 6, 9, and 12 months after the TCR T cell infusion and sent to the Specimen Processing Lab for RCL testing, as per FDA guidelines.

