4. STUDY DESIGN AND INVESTIGATIONAL PLAN

4.1 Design: Phase I/II single-arm dose-escalation non-masked interventional study

The study will be a phase I/II, non-masked (not blinded), interventional study aimed at treating up to 16 HLA*A0201 patients with metastatic MCC that has progressed despite immune checkpoint inhibitor therapy (PD-1 or PD-L1 inhibitor). All patients will receive study interventions.

[figure not shown]
Patients may receive the other, standard-of-care portions of the ATTAC regimen in addition to T cells. This includes the PD-L1 inhibitor avelumab. Please see **Section 6/treatment plan** for further details).

Patients will receive up to two T cell infusions. Please see **6.4.4** for details regarding selection of one versus two cycles of T cell therapy.

Any patient experiencing treatment related grade 3 or 4 toxicity (except for the expected toxicity specifically excepted/outlined in **Section 12.6**) will immediately stop receiving T cell infusions, avelumab, and class I HLA upregulation. They will receive treatment as appropriate for their condition (see **Section 7** and **Section 12**). They will continue to be followed for response/outcome. Patients with infusion reactions to avelumab may receive pembrolizumab for first or subsequent infusions.

As a criterion for enrollment into the trial, participants must agree to biopsies of tumor tissue if medically feasible. A minimum of 4 biopsies will be performed as clinical status allows: prior to interferon gamma administration, 1-2 days prior to T cell infusion, 2 weeks after, and 12 weeks after the first full dose T cell infusions. However, should there be no tumor tissue that is accessible for biopsy, patients will still be considered for participation at discretion of the investigator. Similarly, should an investigator or treating physician determine that a biopsy cannot be performed safely for clinical reasons (e.g., no safe approach), biopsies may be cancelled or retimed at the investigator or treating physician's discretion.

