13.3 Primary Endpoint: Efficacy

13.3.1 Definition of response

Irradiated and non-irradiated lesions will be separately tracked but response determined in totality. As indicated, patients who will be evaluated for this endpoint will have at least one trackable lesion by response evaluation criteria in solid tumors (RECIST) 1.1. Response will be defined as best overall response by RECIST 1.1 of complete or partial response for patients with at least one measurable lesion.

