13.3.2 Definition of success and power of success

Responses to alternative therapies in this population of patients with advanced MCC resistant to PD1-axis blockade are rare, and we therefore will use a 5% response rate as the fixed benchmark upon which we hope to improve with the proposed treatment. If the true response rate with TCR-transduced cells is 25%, 16 patients yield 84% power to detect a statistically significantly improved response rate (one-sided .05) over the fixed rate of 5%. Three or more responses among 16 pts would occur with probability .04 if the true response rate is 5%, so if three or more patients respond (an observed response rate of at least 19%), we will conclude that this regimen is potentially efficacious and worthy of further

study. If power is instead assessed among the anticipated 12 patients who will receive a checkpoint inhibitor, the statistical power is reduced to 78%.

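### Research biopsies, with excision allowed after infusion, are not steered away from RECIST target lesions, and the protocol does not say how a target lesion reduced by biopsy is scored

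*Combined protocol and SAP*

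**What the plan says.** **Biopsies.** Section 4.1 plans serial sampling: "A minimum of 4 biopsies will be performed as clinical status allows". The time points are before interferon gamma, shortly before T cell infusion, and 2 and 12 weeks after infusion. Section 11.3 describes the baseline research sample, if none was kept from a recent clinical biopsy, as "a core needle (6 needle passes) or punch biopsy (1 x 6 mm or 2 x 4 mm") or an equivalent. Section 11.4 adds a research biopsy before infusion to look at class I MHC. Section 11.5 covers the sample at about day 10 to 16, for which patients "will be asked to undergo a punch, excisional or a core biopsy of an accessible tumor", and labels it as research. The 12-week and relapse biopsies are described there as clinical, with an extra portion for research. Appendix B asks for four plus two cores or equivalent, plus any additional tissue, both before treatment and at day 14.

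**Imaging.** Section 11.3 allows the baseline scan up to 45 days before the first infusion. Section 11.6 sets response assessments at 4 and 12 weeks after each infusion.

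**Endpoint.** Section 13.3.1 states: "Response will be defined as best overall response by RECIST 1.1 of complete or partial response", for patients with at least one measurable lesion. It has one lesion-level provision, for irradiated lesions. Section 13.3.2 sets the comparison: "we therefore will use a 5% response rate as the fixed benchmark". Success is three or more responders among 16.

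**The concern.** An excision at week 2 removes tissue that was measured at baseline and will be looked for at week 4. If the lesion is a target, the procedure and the treatment are confounded in the measurement that decides response. No section reserves target lesions, prefers a non-target site, or gives a scoring rule for a lesion that has been cut out or cut down. The authors did make a provision for radiation as a local procedure, so the absence of one for biopsy is a gap rather than a matter of style.

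The design has little room to absorb such an error. There is no control arm in which the same biopsies would produce the same artefact, the benchmark is a fixed 5%, and three responders are enough. One patient wrongly scored as a responder is a third of what success requires.

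**Working it through.** **Inputs from the documents.** N = 16, success at 3 or more responders, null rate 5%, alternative 25%, one-sided 0.05 (section 13.3.2).

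**Input not in the documents.** q, the probability that a patient who would otherwise be a non-responder is scored as a responder because tissue was removed. It is an assumption, shown over a range.

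**Step 1: reproduce the plan's figures.** The plan states: "Three or more responses among 16 pts would occur with probability .04 if the true response rate is 5"%. With X ~ Binomial(16, 0.05):

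P(X ≥ 3) = 1 − [P(0) + P(1) + P(2)] = 1 − (0.4401 + 0.3706 + 0.1463) = 0.043.

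This agrees with the stated .04. The plan also states: "If the true response rate with TCR-transduced cells is 25%, 16 patients yield 84% power". Exact binomial power for 3 of 16 at 25% is 0.803. The 84% is close to an uncorrected normal approximation (0.846). That difference is a separate matter and does not affect what follows.

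**Step 2: timing.**

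| Event | Time relative to first infusion |
|---|---|
| Baseline scan (11.3) | up to 45 days before |
| Pre-infusion research biopsy (4.1, 11.4, Appendix A note) | day of infusion to 2 days before, depending on the section |
| 2-week research biopsy (11.5) | about day 10 to 16 |
| First response read (11.6) | week 4 |
| Second response read (11.6) | week 12 |

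The 2-week biopsy always lies between the baseline scan and the first response read. The pre-infusion biopsy lies there whenever the baseline scan precedes it. The pre-interferon sample may come before or after the baseline scan.

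**Step 3: false-positive probability with an artefact rate q.** At a true 5% rate, the chance that a patient is scored as a responder becomes p = 0.05 + 0.95q. The false-positive probability is P(X ≥ 3) with X ~ Binomial(16, p).

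| q (assumed) | p | P(X ≥ 3) |
|---|---|---|
| 0 | 0.0500 | 0.043 |
| 0.5% | 0.0548 | 0.054 |
| 1% | 0.0595 | 0.066 |
| 2% | 0.0690 | 0.094 |
| 5% | 0.0975 | 0.200 |
| 10% | 0.1450 | 0.416 |

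The exact level starts at 0.043, so an artefact rate of 0.5% already takes it past 0.05.

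**Step 4: conditional view.** If exactly one of the 16 is a responder only because of the procedure, two of the other 15 suffice: P(X ≥ 2 | 15, 0.05) = 1 − (0.4633 + 0.3658) = 0.171. This is conditional on the artefact having occurred.

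**The case against.** The strongest reply is that the gap is silence, not an instruction. No sentence says target lesions will be biopsied. Excision is named only for the biopsies after infusion in section 11.5, the baseline sample is by core, punch or equivalent, and Appendix B is written mainly in cores, which remove little tissue. Biopsies are subject to clinical status, are waived where no tumor is amenable, and may be cancelled or retimed. The 12-week biopsy is clinical and is interpreted in light of whether tumors are growing or shrinking, so it most naturally follows the week 12 read and would not create shrinkage on it. The endpoint adopts RECIST 1.1 by reference, and that standard may have its own rule. All of this stands, and it limits the point to the pre-infusion and 2-week research biopsies and to excision or a punch of a small lesion.

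Some stronger readings are tempting but not supported:

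- A reader might infer that every patient has four biopsies by punch, excision or six-pass core. That merges provisions that apply to different samples.
- A reader might infer that where only one lesion is accessible, it must be the target. Accessible for biopsy is not the same as measurable or selected, and these patients may have other measurable disease.
- A reader might take 0.171 as the trial's false-positive rate. It assumes an event whose frequency the documents do not give.
- A reader might infer a definite power loss because swelling after biopsy hides a true response. The documents give no basis for its frequency. The scenario also needs care: if one true response is hidden, four are needed, P(X ≥ 4 | 16, 0.25) = 0.595. The figure 0.764 = P(X ≥ 3 | 15, 0.25) answers a different question, the loss of one patient of unknown outcome.

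What remains is that the plan, followed as written, permits excision of a measured lesion between baseline and the first response read and does not itself say what to do with the measurement.

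**Conclusion.** The point holds in this limited form. It does not show that the primary result will be biased, because neither the frequency of excision nor that of target-lesion sampling is stated. It shows that the 3-of-16 rule tolerates very little of either: its exact false-positive probability of 0.043 goes to 0.066, 0.094 or 0.200 for assumed artefact rates of 1%, 2% or 5%. These figures rest on independent patients, all 16 evaluable for response, and an artefact that acts only on patients who would otherwise be non-responders. The absence of a scoring rule is established for the protocol text only. The change is worth making because it is cheap and is best settled before responses are read.

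**What to change.** 1. In sections 11.3 to 11.5, require that RECIST target lesions be selected at baseline before biopsy sites are chosen. Take the pre-infusion and 2-week research tissue from a non-target lesion where one is accessible. Exempt the clinically driven 12-week and relapse biopsies, which have to sample the lesion in question.
2. In section 13.3.1, require that any target lesion excised or substantially reduced by biopsy be flagged, and state that the reduction does not count towards partial or complete response. One workable rule is to drop that lesion from both the baseline and the follow-up sums. Lesions sampled only by core should continue to be measured as usual. Carrying forward the pre-biopsy diameter is not advisable: it would freeze the lesion, hide real progression in it, and make a patient with a single target unable to respond.
3. Report, as a sensitivity analysis, the 3-of-16 result with every patient whose response depends on such a lesion set to non-responder.

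The cost is wording in four sections and a flag on the tumour-measurement form. Some research samples will come from less convenient lesions, and a patient whose only target is excised may not be countable as a responder. No planned biopsy is lost.
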